6.4 Efficacy and Safety Variables

6.4.1 *Efficacy Variables*

The following assessment measures will be conducted to evaluate the efficacy of BBI-4000:

- HDSM-Ax as measured by the subject

- GSP by the investigator
- HDSS as measured by the subject
- DLQI as measured by the subject

6.4.1.1 *Primary Efficacy Variables*

The primary efficacy endpoint is improvement on the HDSM-Ax, defined as:

1. The proportion of subjects achieving at least a 1-point improvement in HDSM-Ax from baseline to end of therapy.
2. Change of HDSM-Ax from baseline to end of therapy as a continuous measure

6.4.1.2 *Secondary Efficacy Variables*

Secondary efficacy endpoints include the following:

1. The proportion of subjects achieving at least a 2-point improvement in HDSM-Ax from baseline to end of therapy.
2. The proportion of subjects achieving at least a 50% reduction in gravimetrically measured sweat production (both axilla combined) from baseline to end of therapy.
3. The absolute change from baseline in gravimetrically measured sweat production to end of therapy.
4. The percent change from baseline in gravimetrically measured sweat production to end of therapy.
5. The ranked change from baseline in gravimetrically measured sweat production to end of therapy.
6. The proportion of subjects achieving at least a 1-point improvement in the HDSM-Ax score and at least 50% reduction in gravimetrically measured sweat production from baseline to end of therapy.
7. The proportion of subjects achieving at least a 2-point improvement in the HDSM-Ax total score and at least 50% reduction in gravimetrically measured sweat production from baseline to end of therapy.
8. The proportion of subjects achieving at least a 2-point improvement in HDSS from baseline to end of therapy.

9. The proportion of subjects achieving at least a 1-point improvement in HDSS from baseline to end of therapy.

6.4.1.3 *Other Efficacy Variables*

Other efficacy endpoints are:

1. The proportion of subjects achieving at least a 1-point improvement in the HDSM-Ax score from baseline to Days 8, 15, 22, 29, 36, 41, 42, 43, and 57.
2. Change in HDSM-Ax from baseline to Days 8, 15, 22, 29, 36, 41, 42, 43, and 57 as a continuous measure
3. The proportion of subjects achieving at least a 2-point improvement in the HDSM-Ax score from baseline to Days 8, 15, 22, 29, 36, 41, 42, 43, and 57.

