The primary efficacy endpoint is the change from baseline to the end of therapy in the mean HDSM-Ax score. The primary efficacy endpoint will be analyzed both as a continuous measure and as a binary outcome. As a continuous measure, the HDSM-Ax change scores will be compared between treatment groups in pairwise fashion by an ANCOVA model adjusting for the baseline HDSM-Ax score. The analysis will be performed with no imputation of missing data. As a binary measure, i.e. achieving a ≥ 1 -point improvement or not from baseline to end of therapy, a binary logistic regression will be performed with treatment assignment and baseline HDSM-Ax score as independent variables in the model. Any subject without a definable 1-point improvement (e.g., missing data) between Baseline and End of Treatment will be considered a non-responder. P values will generally be regarded as descriptive and statistical significance will be assessed using a gate-keeping hierarchy as described in Section [7.4.6.5](#) for both the continuous measure and binary data analyses.

The null hypothesis to be tested for the continuous measure is as below:

$$H_0: \mu_A \geq \mu_P;$$

where μ_A and μ_P represent the true underlying mean change scores for Treatment A (active drug) and Treatment P (vehicle), respectively. The alternate hypothesis to be tested is that the true active treatment group mean change score is smaller than the true vehicle group mean change score:

$$H_1: \mu_A < \mu_P;$$

Tested in the logit scale, the null hypothesis for the dichotomous outcome is that the true proportion of subjects with a 1 point or more improvement is lower in the active treatment group:

$$H_0: P_A \leq P_P;$$

The alternate hypothesis to be tested is that the true proportion of subjects with a 1 point or more improvement is higher in the active treatment group:

$$H_1: P_A > P_P;$$

7.4.4.2 *Sensitivity Analysis by Mixed Effects Models*

As a method that is known to be robust to missing data, mixed model repeated measures (MMRM) analyses will also be performed for the primary efficacy endpoint using all available HDSM-Ax change from baseline data on study days 8, 15, 22, 29, 36, and end of therapy. As fixed effects, treatment (active treatment group or vehicle gel), baseline HDSM-Ax score and visit (included in the class statement as a class variable) and baseline*visit interactions will be

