included in the model both without and with treatment*visit interaction terms. Subject will be analyzed as a random effect. Similarly, MMRMs will also be performed for the primary efficacy endpoint using HDSM-Ax dichotomized response data, and HDSM-Ax + GSP dichotomized response data. The models will be the same as the model for continuous data but the dependent variable of interest will be the response status with a logit link, using the SAS Proc GLIMMIX module. Both the heterogeneous CS (CSH) and TOEP (TOEPH) covariance structures will be considered and the structure with lower AIC will be used. The percentage of responders will also be summarized at each visit in the result table.

MMRM analysis as described above will also be performed for continuous GSP data (both Normal model and using rank transformed data) and binary GSP response (i.e. 50% reduction from baseline) data.

7.4.4.3 *Additional Sensitivity Analysis*

An additional sensitivity analysis will be performed as follows. For subjects missing all 3 end of therapy values, the data will be imputed by the last three available post-baseline (i.e., from Day 8 onward) assessment values. This analysis will be performed for both the continuous data analysis and the binary data analysis using the same ANCOVA models as described above.

7.4.5 *Secondary and Other Efficacy Endpoint Analysis Methods*

Baseline and End of Therapy values for HDSS and GSP are defined as follows.

HDSS:

- Baseline value = average of two screening values, i.e., Visit 1 and Visit 4
- End of Therapy value = average of Days 41, 42, and 43 measurements, i.e., Visit 11, Visit 12, and Visit 13, respectively.
- End of Therapy Imputed value = includes subjects missing all end of therapy values, where data is imputed by the last three available post-baseline visits.

Gravimetric Sweat Production (both axilla combined total):

- Baseline value = the median of GSP1, GSP2, and GSP3 measurements obtained on Visit 2, Visit 3, and Visit 4, respectively. The mean value of the same visits will also be used for analysis.
- End of Therapy value = the median of GSP4, GSP5, and GSP6 measurements obtained on Visit 11, Visit 12, and Visit 13, respectively. The mean value of the same visits will also be used for analysis.

- End of Therapy Imputed value = includes subjects missing all end of therapy values, where data is imputed by the last three available post-baseline visits.

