7.4.6 Statistical/Analytical Issues

7.4.6.1 Adjustments for Covariates

The ANCOVA model and binary logistic regression model to compare treatment groups for the primary endpoint will include a covariate adjustment for the baseline value. Select secondary endpoints will be analyzed similarly.

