HDSM-Ax and GSP Parameters	Time Point	Vehicle	BBI-4000 5%	
		(N=)	(N=)	P-value ^[1]
		n (%)	n (%)	
HDSM-Ax reduction from Baseline ^[2] ≥ 1 and GSP reduction from Baseline ^[2] ≥ 50%	Day 8	n (x.x%)	n (x.x%)	x.xxxx
	Day 15	n (x.x%)	n (x.x%)	x.xxxx
	Day 22	n (x.x%)	n (x.x%)	x.xxxx
			
	End of Therapy ^[3]	n (x.x%)	n (x.x%)	x.xxxx
	MMRM treatment p-value ^[4]			x.xxxx
	MMRM treatment*visit p-value ^[5]			x.xxxx
HDSM-Ax reduction from Baseline ^[2] ≥ 2 and GSP reduction from Baseline ^[2] ≥ 50%				
....				

Abbreviations: GSP, gravimetrically measured sweat production; HDSM-Ax, Hyperhidrosis Disease Severity Measure-Axillary; mITT, Intent-to-Treat; MMRM, mixed model for repeated measures

Note: Responder is defined as a subject who achieved the reduction in HDSM-Ax score specified in the HDSM-Ax Parameter column, between Baseline and End of Therapy. Subjects without a defined improvement in score are considered non-responders.

^[1] P-values comparing active treatment to vehicle are based on a binary logistic regression model where treatment and baseline HDSM-Ax Score are predictors.

^[2] HDSM-Ax baseline is defined as the average of any available Visit 1 (Screening) and Visit 4 (Rescreening) values; GSP baseline is defined as the median of any available GSP measurements from Visit 2, Visit 3, and Visit 4.

^[3] HDSM-Ax End of Therapy is defined as the average any available Day 41, Day 42, and Day 43 values; GSP End of Therapy is defined as the median of any available GSP measurements from Day 41, Day 42, and Day 43.

^[4] P-values comparing active dose to vehicle are based on an MMRM with subject as a random effect, treatment, protocol-specified visit, baseline, and baseline*visit interaction as fixed effects.

^[5] P-value is for the collective treatment*visit interactions based on an MMRM with subject as a random effect, and treatment, protocol-specified visit, treatment*visit interaction, baseline, and baseline*visit interactions as fixed effects.

Reference: Listing #(s)

Path\filename.sas dddmmyyy hh:mm

Programming Notes: Continue for Days 29, 36, 41, 42, 43, 57, HDSM-Ax ≥ 2, and remaining BBI-4000 dose groups (10%, 15%); Repeat as Table 14.2.2.2 HDSM-Ax and GSP Responder MMRM (PP Population). MMRM = generalized linear mixed model for repeated measures, with logit linkage. For MMRM analyses, use data on Days 8, 15, 22, 29, 36 and End of Therapy.

Table 14.2.3.1
GSP Summary of First and Last Visits
mITT Population

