- Repeat tables with ranked values. Rank continuous data low-to-high within each visit, disregarding treatment, and use average for ties.
- Repeat for Table 14.2.3.11 GSP Change from Baseline MMRM and Change from Baseline by Visit ANCOVA for Ranked Values (mITT Population)
- Repeat for Table 14.2.3.12 GSP Change from Baseline MMRM and Change from Baseline by Visit ANCOVA for Ranked Values (PP Population)

Table 14.2.3.13
GSP Responder MMRM
mITT Population

Time Point	Type of Average ^[1]	Vehicle	BBI-4000 5%		BBI-4000 10%		BBI-4000 15%	
		(N=)	(N=)	(N=)	(N=)	(N=)	(N=)	
		n (%)	n (%)	P-value ^[2]	n (%)	P-value ^[2]	n (%)	P-value ^[2]
Day 8	Median	n (x.x%)	n (x.x%)	x.xxxx	n (x.x%)	x.xxxx	n (x.x%)	x.xxxx
Day 15		n (x.x%)	n (x.x%)	x.xxxx	n (x.x%)	x.xxxx	n (x.x%)	x.xxxx
Day 22		n (x.x%)	n (x.x%)	x.xxxx	n (x.x%)	x.xxxx	n (x.x%)	x.xxxx
....								
End of Therapy ^[3]		n (x.x%)	n (x.x%)	x.xxxx	n (x.x%)	x.xxxx	n (x.x%)	x.xxxx
MMRM treatment p-value ^[4]				x.xxxx		x.xxxx		x.xxxx
MMRM treatment*visit p-value ^[5]				x.xxxx		x.xxxx		x.xxxx

Abbreviations: GSP, gravimetrically measured sweat production; mITT, Intent-to-Treat; MMRM, mixed model for repeated measures

Note: Responder is defined as a subject who achieved a reduction in GSP of at least 50% between Baseline and End of Therapy. Subjects without a defined improvement in score are considered non-responders.

^[1] Method of calculating average for Baseline and End of Therapy.

^[2] P-values comparing active treatment to vehicle are based on a binary logistic regression model where treatment and baseline GSP are predictors.

^[3] End of Therapy is defined as the median/mean of any available Day 41, Day 42, and Day 43 values.

^[4] P-values comparing active dose to vehicle are based on a logit-linked MMRM with subject as a random effect, treatment, protocol-specified visit, baseline, and baseline*visit interaction as fixed effects.

^[5] P-value is for the collective treatment*visit interactions based on a logit-linked MMRM with subject as a random effect, and treatment, protocol-specified visit, treatment*visit interaction, baseline, and baseline*visit interactions as fixed effects.

Reference: Listing #(s)

Path\filename.sas ddmmmyyyy hh:mm

Programming Notes:

- Continue for Days 29, 33, 41, 42, 43, 57. Repeat analysis with mean method for calculating Baseline and EoT.
- MMRM = generalized linear mixed model for repeated measures, with logit linkage.

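### The composite HDSM-Ax plus GSP responder model adjusts for baseline HDSM-Ax but not baseline GSP: adding it is a cheap, low-priority improvement

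*SAP*

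**What the plan says.** SAP 6.4.1.2 lists two composite secondary endpoints, one with a 1-point and one with a 2-point HDSM-Ax threshold. The first reads "The proportion of subjects achieving at least a 1-point improvement in the HDSM-Ax score and at least 50% reduction in gravimetrically measured sweat production". SAP 6.4.1.3 repeats both at each post-baseline study day.

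For these endpoints Table 14.2.2.1 (mITT, repeated for the PP Population as Table 14.2.2.2) specifies, in footnote 1, a "binary logistic regression model where treatment and baseline HDSM-Ax Score are predictors". Footnote 2 of the same table states that "GSP baseline is defined as the median of any available GSP measurements from Visit 2, Visit 3, and Visit 4", so the covariate already exists in the analysis data. Where the 50% GSP criterion stands alone, Table 14.2.3.13, footnote 2, uses a "binary logistic regression model where treatment and baseline GSP are predictors".

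For the repeated-measures version, SAP 7.4.4.2 lists "baseline HDSM-Ax score and visit" among the fixed effects of the continuous model. It then says of the dichotomised HDSM-Ax and HDSM-Ax plus GSP responses: "The models will be the same as the model for continuous data". Footnotes 4 and 5 of Table 14.2.2.1 say only *baseline*, without saying which. SAP 7.4.6.1 says the primary models "will include a covariate adjustment for the baseline value" and that select secondary endpoints are treated similarly. The randomisation described in SAP 6.3.2 is 1:1:1:1 by next available kit number, with no stratification on GSP.

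**The concern.** The composite has two components, and the model adjusts for the baseline of only one. The SAP treats baseline GSP as the relevant covariate when the 50% reduction is analysed alone, then drops it without explanation when the same criterion sits inside the composite. Footnote 1 matches the footnote in the HDSM-Ax responder table (14.2.1.7), so it may have been carried over; that is an inference.

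Baseline GSP can predict a 50% fall even though response is scored against the subject's own baseline. A baseline that is high by chance tends to be followed by a lower value, which makes the threshold easier to reach. If the arms differ by chance in baseline GSP, the unadjusted comparison is tilted. All three active arms share one vehicle group, so an atypical vehicle baseline would tilt all three comparisons the same way. If the gap is noticed only after unblinding, adding the covariate becomes a post hoc choice.

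**Working it through.** **Design inputs (SAP 7.6 and 7.1.1).** 50 evaluable subjects per arm; one-sided alpha 0.10; assumed rates of 75% and 50% for the primary binary endpoint. The documents give no power figure for the composite, so the design figure is reproduced first to confirm the inputs.

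- Null SE = sqrt(2 × 0.625 × 0.375 / 50) = 0.0968. Alternative SE = sqrt((0.1875 + 0.25) / 50) = 0.0935.
- Uncorrected power: Φ((0.25 − 1.2816 × 0.0968) / 0.0935) = 0.911.
- Continuity-corrected (subtract 1/50): Φ((0.23 − 0.1241) / 0.0935) = 0.871. Fisher's exact test gives 0.864. Both agree with the stated 0.87.
- Continuous endpoint: 0.888 against the stated 0.89.

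**How often imbalance arises.** The SD of the standardised baseline difference is sqrt(2/50) = 0.20. A difference of at least 0.2 SD in either direction has probability 2 × (1 − Φ(1)) = 0.317, or about 16% on each side. At least 0.3 SD in either direction occurs in 13% of comparisons, and at least 0.4 SD in 5%.

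**Effect with an assumed direct association.** The documents give no link between baseline GSP and response, so it was varied: 0, 0.25, 0.5 or 0.8 log-odds per SD. Vehicle response was set at 35% and the HDSM-Ax baseline effect at 0.2 per SD, with 6,000 trials per scenario. Each cell shows the rejection rate without / with baseline GSP in the logistic model.

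| Log-odds per SD | Null, all trials | Null, active ≥0.2 SD higher | Null, active ≥0.2 SD lower | Power (log-OR 1.0) |
|---|---|---|---|---|
| 0 | 0.098 / 0.101 | 0.095 / 0.095 | 0.102 / 0.108 | 0.880 / 0.877 |
| 0.25 | 0.099 / 0.102 | 0.126 / 0.107 | 0.072 / 0.098 | 0.875 / 0.880 |
| 0.5 | 0.094 / 0.100 | 0.156 / 0.102 | 0.045 / 0.094 | 0.855 / 0.870 |
| 0.8 | 0.102 / 0.100 | 0.220 / 0.103 | 0.028 / 0.104 | 0.807 / 0.849 |

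Each conditional cell rests on about 0.16 × 6,000 ≈ 950 trials, so its Monte Carlo SE is about sqrt(0.1 × 0.9 / 950) ≈ 0.01. The shift in log-OR per 0.2 SD of imbalance was 0.057, 0.094 and 0.153 under the null, close to 0.2 times the association (0.05, 0.10, 0.16).

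**Effect when the association arises only from measurement noise and entry selection.** Between/within-subject log SDs of 0.6/0.4, 0.7/0.55 and 0.9/0.7 were assumed. With the 150 mg combined-total entry rule imposed (4,000 trials per setting), null rejection was 0.137, 0.185 and 0.157 when active started more than 0.2 SD higher, and 0.075, 0.060 and 0.059 when it started lower. With baseline GSP added, it was 0.095–0.116 and 0.099–0.111. Unconditional error without the covariate was 0.104–0.108. Other runs with variance inputs of this kind gave 0.13–0.18 and 0.05–0.08 without the covariate and about 0.10–0.13 with it. Power gains in the variance-based runs were about 0 to 1 point (for example 0.728 to 0.734).

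**The case against.** A reader might infer that the composite p-values have inflated type I error. The documents and the calculations do not support that. Randomisation protects the unconditional error, which stays near 0.10 with or without the covariate. The 32% of comparisons with a 0.2 SD imbalance split evenly: half inflate the error and half deflate it. In a separate set of null simulations with composite rates of 0.07–0.14, the two models gave different verdicts in only about 3% of trials.

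The stakes are limited. The hierarchical testing in SAP 7.4.6.5 covers the primary HDSM-Ax analyses, not the composites, and SAP 7.4.4.1 calls p-values generally descriptive. The GSP component also has its own baseline-adjusted responder and ANCOVA analyses, which would show whether GSP imbalance is driving a composite result. The composite model is prespecified and follows Protocol 10.3, which models secondary analyses on the binary HDSM-Ax analysis.

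The selection argument is real but weakened by design. The GSP floor must be met at Visit 1, which is outside the baseline, and at only one of Visits 2 to 4; the baseline is then a median of three measurements.

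For the GLIMMIX the text is less clear-cut than for the logistic model. SAP 7.4.4.2 also applies the model to GSP outcomes, where the baseline term must change, and footnotes 4 and 5 do not name it. That part is best treated as wording to clarify.

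All of this stands and sets the priority. It does not explain why the covariate used for the GSP-only responder is absent from the composite.

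**Conclusion.** The omission in footnote 1 is explicit, and no section of either document adds baseline GSP to a composite model. The consequence is some loss of precision and of protection against chance imbalance on two secondary endpoints and their by-visit versions. The primary analysis, the sample size and the dose-testing order are unaffected.

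The size is conditional. Under the assumed variances, null rejection is about 0.13–0.18 in the roughly 16% of comparisons where active starts more than 0.2 SD higher, and about 0.05–0.08 in the roughly 16% where it starts lower. An assumed direct association of 0.8 log-odds per SD widens this to 0.22 and 0.03, with a power gain of about 4 points; an association of zero removes the effect. The documents supply neither the GSP variance nor the association, so confidence is high in the textual point and moderate at best in the magnitude.

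Cheap improvement, low priority.

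**What to change.** In the logistic and GLIMMIX models for Tables 14.2.2.1 and 14.2.2.2, include both baseline HDSM-Ax and baseline GSP. Use the GSP baseline already defined in footnote 2, entered as in the GSP responder model. Name both baselines in footnotes 1, 4 and 5, and make SAP 7.4.4.2 agree. Do this before unblinding.

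The cost is one parameter in each logistic model. In the GLIMMIX it is up to six: one main effect plus five interaction terms over six time points (Days 8, 15, 22, 29, 36 and end of therapy), if baseline GSP by visit is included. Where responders are sparse, as is likely for the 2-point composite, use the baseline GSP main effect only. The adjusted odds ratio is also a slightly different quantity: at the strongest assumed association the mean estimated log-OR was 0.90 without the covariate and 1.05 with it. The tables should therefore state the covariates plainly.

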APPENDIX C: LISTING LAYOUTS

Listing 16.17
Randomization Scheme and Codes

Subject ID	Randomization Number	Treatment Group Code	Treatment Group	Treatment Group Description
xxx-xxxx	xxxx	A /	Vehicle /	Vehicle gel /
		B /	BBI-4000 5% /	5% BBI-4000 in vehicle gel /
		C /	BBI-4000 10% /	10% BBI-4000 in vehicle gel /
		D	BBI-4000 15%	15% BBI-4000 in vehicle gel
xxx-xxxx				
...				

Path\filename.sas ddmmmyyyy hh:mm

**Listing 16.2.1
Subject Disposition**

Subject ID	Treatment Group	Safety Population ^[1]	mITT Population ^[2]	PP Population ^[3]	Date of First Dose	Study Exit Date (Study Day ^[4])	Complete Treatment?	Reason Subject Did Not Complete Treatment	Complete Study?	Primary Reason for Early Termination
xxx-xxxx	Vehicle / BBI-4000 5% / BBI-4000 10% / BBI-4000 15%	Yes / No	Yes / No	Yes / No	ddMMMyyyy	ddMMMyyyy (xx)	Yes / No	Adverse Event / Withdrawal by Subject / Physician Decision / Protocol Violation / Lost to Follow-Up / Death / Pregnancy / Worsening Condition / Lack of Efficacy / Study Termination by Sponsor / Other	Yes / No	Normal Study Completion / Adverse Event / Withdrawal by Subject / Physician Decision / Protocol Violation / Lost to Follow-Up / Death / Pregnancy / Worsening Condition / Lack of Efficacy / Study Termination by Sponsor / Other
xxx-xxxx	...									

Abbreviations: mITT, Intent-to-Treat; PP, Per-Protocol

^[1] Safety population includes all subjects randomized in the study who received study drug at least once. Treatment group assignment is based on the treatment actually received.

^[2] mITT population includes all subjects who were randomized and dispensed study drug. Treatment group assignment is based on the planned treatment assigned.

^[3] PP population includes all Safety subjects who meet all inclusion/exclusion criteria, have not taken/applied prohibited concomitant medications, and have full data collected for all GSP visits.

^[4] Time (days) relative to date of first dose of study drug

Path\filename.sas ddmmmyyyy hh:mm

Listing 16.2.2.1
Protocol Violations/Deviations

Subject ID	Treatment Group	Date of Deviation (Study Day ^[1])	Major Protocol Violation?	Deviation/Violation Category	Reason for Deviation/Violation	Date of Sponsor Approval
xxx-xxxx	Vehicle / BBI-4000 5% / BBI-4000 10% / BBI-4000 15%	ddMMMyyyy (xx)	Yes / No	Category	Deviation	ddMMMyyyy
xxx-xxxx	...					

[1] Time (days) relative to date of first dose of study drug

Path\filename.sas ddmmmyyyy hh:mm

**Listing 16.2.2.2
Informed Consent and Eligibility Criteria**

Subject ID	Treatment Group	Subject Sign		Time Informed Consent Signed	Protocol Version	Does subject meet all eligibility criteria?	If No, Criterion Not Met	Inclusion/Exclusion Criteria Waivers		
		Informed Consent?	Date Informed Consent Signed					Was Waiver Granted?	Date of Waiver	Who Granted the Waiver?
xx-xxx	Vehicle / BBI-4000 5% / BBI-4000 10% / BBI-4000 15%	Yes / No	ddMMMyyyy	hh:mm	Original November 22, 2016 / Version 1 22FEB2017	Yes / No	Inclusion # / Exclusion #	Yes / No	ddMMMyyyy	Text
							Inclusion # / Exclusion #	Yes / No	ddMMMyyyy	Text
							...			
xx-xxx										

Path\filename.sas ddmmmyyyy hh:mm

Listing 16.2.3
Subjects Excluded from the Efficacy Analysis

Subject ID	Treatment Group	mITT Population ^[1]	PP Population ^[2]	Reason for Exclusion from the Efficacy Analysis
xx-xxx	Vehicle / BBI-4000 5% / BBI-4000 10% / BBI-4000 15%	Yes / No	Yes / No	Reason (e.g., screen failure, subject did not receive study drug, protocol violation, etc.), including any relevant specifications
xx-xxx				
...				

Abbreviations: mITT, Intent-to-Treat; PP, Per-Protocol

^[1] mITT population includes all subjects who were randomized and dispensed study drug. Treatment group assignment is based on the planned treatment assigned.

^[2] PP population includes all Safety subjects who meet all inclusion/exclusion criteria, have not taken/applied prohibited concomitant medications, and have full data collected for all GSP visits.

Path\filename.sas ddmmmyyy hh:mm

**Listing 16.2.4.1
Demographics**

Subject ID	Treatment Group	Date of Birth	Age (years)	Sex	If Female, is subject of childbearing potential?	Ethnicity	Race
xxx-xxxx	Vehicle / BBI-4000 5% / BBI-4000 10% / BBI-4000 15%	ddMMMyyyy	xx	Male / Female	Yes / No	Hispanic or Latino / Not Hispanic or Latino	American Indian or Alaska Native / Asian / Black or African American / Native Hawaiian or Other Pacific Islander / White / Other
xxx-xxxx							
...							

Path\filename.sas ddmmmyyyy hh:mm

Programming Note: If multiple races are reported for a given subject, display all that are reported in the "Race" column, separated by a semicolon.

**Listing 16.2.4.2
Medical History**

Subject ID	Treatment Group	System Organ Class ^[1]	Condition	Onset Date	Resolution Date
xxx-xxxx	Vehicle / BBI-4000 5% / BBI-4000 10% / BBI-4000 15%	Body System Body System ...	Condition / Diagnosis / Surgery	ddMMMyyyy	ddMMMyyyy / Ongoing
xxx-xxxx	...				

^[1] Medical history events are coded to system organ class using the Medical Dictionary for Regulatory Activities (MedDRA), version 19.1.

Path\filename.sas ddmmmyyyy hh:mm

Programming Note: Sort conditions based on onset date. If partial onset dates are reported (e.g., month and year only), separate out the portions of the date to sort separately by year, then month, then day.

**Listing 16.2.5.1
Study Drug Dosing**

Subject ID	Treatment Group	Start of Study Drug Administration	End of Study Drug Administration (Study Day ^[1])	Any Application Deviations?	Deviation Start Date (Study Day ^[1])	Deviation End Date (Study Day ^[1])	Deviation Type	Axilla	Reason for Deviation
xxx-xxxx	Vehicle / BBI-4000 5% / BBI-4000 10% / BBI-4000 15%	ddMMMyyyy	ddMMMyyyy (xx)	Yes / No / Unknown	ddMMMyyyy (xx)	ddMMMyyyy (xx)	Missed / Other (specify)	Right / Left / Both	Adverse Event / Other (specify)
xxx-xxxx	...								

^[1] Time (days) relative to date of first dose of study drug

Path\filename.sas ddmmmyyyy hh:mm

Listing 16.2.5.2
Study Drug Administration and Accountability

Subject ID	Treatment Group	Pump Container	Pump Dispensed?	If No, Specify	Date Dispensed (Study Day ^[1])	Kit #	Dispensed Weight (g)	Pump Returned?	If No, Specify	Date Returned (Study Day ^[1])	Returned Weight (g)
xxx-xxxx	Vehicle / BBI-4000 5% / BBI-4000 10% / BBI-4000 15%	1	Yes / No	text	ddMMMyyyy (xx)	xxxx	xx.x	Yes / No	text	ddMMMyyyy (xx)	xx.x
		2									
xxx-xxxx	...										

^[1] Time (days) relative to date of first dose of study drug

Path\filename.sas ddmmmyyyy hh:mm

Listing 16.2.5.3
Study Drug Exposure and Compliance

Subject ID	Treatment Group	Expected Number of Doses	Actual Number of Doses	Study Drug Compliance (%) ^[1]	Duration of Exposure (Days) ^[2]	Total Drug Delivered (g) ^[3]
xxx-xxxx	Vehicle / BBI-4000 5% / BBI-4000 10% / BBI-4000 15%	xx	xx	xx.x	ddMMMyyyy (xx)	xxxx
xxx-xxxx	...					

^[1] Study drug compliance is calculated as the number of doses received / the expected number of doses x 100

^[2] Duration of exposure to study treatment is calculated as the date of last dose of study drug – the date of first dose of study drug + 1.

^[3] Total drug delivered is calculated as total grams dispensed – total grams returned.

Path\filename.sas ddmmmyyyy hh:mm

Listing 16.2.6.1
Hyperhidrosis Disease Severity Measure-Axilla
Part 1 of 2

Question Number	Question Text	Responses
1a	Since you woke up yesterday, how often did you experience damp or wet clothing because of your underarm sweating while you were awake?	0-None of the time 1-Almost none of the time, 2-Some of the time, 3-Most of the time 4-All of the time
1b	Since you woke up yesterday, how often did you experience underarm sweating for no apparent reason while you were awake?	0-None of the time 1-Almost none of the time, 2-Some of the time, 3-Most of the time 4-All of the time
2a	Since you woke up yesterday, how severe was your experience with underarm sweating when you felt nervous, stressed or anxious?	0-I did not experience this 1-Mild 2-Moderate 3-Severe 4-Very severe
2b	Since you woke up yesterday, how severe was your experience with damp or wet clothing because of your underarm sweating?	0-I did not experience this 1-Mild 2-Moderate 3-Severe 4-Very severe

Path\filename.sas ddmmmyyyy hh:mm

Programming Note: Listing continues on next page

Listing 16.2.6.1
Hyperhidrosis Disease Severity Measure-Axilla
Part 1 of 2

Question Number	Question Text	Responses
2c	Since you woke up yesterday, how severe was your experience with underarm sweating after almost none or no physical exercise?	0-I did not experience this 1-Mild 2-Moderate 3-Severe 4-Very severe
2d	Since you woke up yesterday, how severe was your experience with underarm wetness?	0-I did not experience this 1-Mild 2-Moderate 3-Severe 4-Very severe
2e	Since you woke up yesterday, how severe was your experience with underarm sweating for no apparent reason?	0-I did not experience this 1-Mild 2-Moderate 3-Severe 4-Very severe
2f	Since you woke up yesterday, how severe was your experience with underarm sweating that was unmanageable?	0-I did not experience this 1-Mild 2-Moderate 3-Severe 4-Very severe

Path\filename.sas ddmmmyyyy hh:mm

Programming note: Listing continues on next page.

Listing 16.2.6.1
Hyperhidrosis Disease Severity Measure-Axilla
Part 1 of 2

Question Number	Question Text	Responses
2g	Since you woke up yesterday, how severe was your experience with underarm sweating when you were cool?	0-I did not experience this 1-Mild 2-Moderate 3-Severe 4-Very severe
3a	Since you woke up yesterday, describe your feeling the need to change clothes because of underarm sweating?	0-Not at all 1-Slight, 2-Moderate 3-Strong 4-Very strong
3b	Since you woke up yesterday, describe your feeling the need to wipe sweat from your underarms?	0-Not at all 1-Slight, 2-Moderate 3-Strong 4-Very strong

Path\filename.sas ddmmmyyyy hh:mm

Programming note: Listing continues on next page.

Listing 16.2.6.1
Hyperhidrosis Disease Severity Measure-Axilla
Part 1 of 2

Question Number	Question Text	Responses
4	Since you woke up yesterday, how much of the time did you experience excessive underarm sweating while you were awake?	0-None of the time 1-Almost none of the time 2-Some of the time 3-Most of the time 4-All of the time
5	How severe was your underarm sweating at its worst since you woke up yesterday?	0-I did not have underarm sweating (completely dry) 1-I had underarm sweating but it was mild (moist) 2-I had underarm sweating and it was moderate (damp) 3-I had underarm sweating and it was severe (wet) 4-I had underarm sweating and it was very severe (soaking)
6	How normal was your level of physical exercise and stress since you woke up yesterday? choose all that apply:	It was a normal day in terms of physical exercise or stress. I experienced more physical exercise than usual. I experienced more nervousness, stress, or anxiety than usual. I experienced less physical exercise than usual. I experienced less nervousness, stress, or anxiety than usual.

Path\filename.sas ddmmmyyyy hh:mm

Listing 16.2.6.1
Hyperhidrosis Disease Severity Measure-Axilla
Part 2 of 2

Subject ID	Treatment Group	Visit	HDSM-Ax Completed?	Assessment Date (Study Day ^[1])	HDSM-Ax Scoring Questions											4	5	6	
					1a	1b	2a	2b	2c	2d	2e	2f	2g	3a	3b				Mean ^[2]
xxx-xxxx	Vehicle / BBI-4000 5% / BBI-4000 10% / BBI-4000 15%	Visit 1 (Screening)	Yes / No	ddMMMyyyy (xx)	0-4	0-4	0-4	0-4	0-4	0-4	0-4	0-4	0-4	0-4	0-4	0-4	0-4	0-4	text
		Visit 4 (Rescreening)																	
		...																	
xxx-xxxx																			

Abbreviation: HDSM-Ax, Hyperhidrosis Disease Severity Measure-Axilla

Note: Questions Q1a-Q5 specify one response per question; Q6 may respond with all that apply.

^[1] Time (days) relative to date of first dose of study drug

^[2] Mean is calculated as the total score for questions 1 through 3 (11 sub-items) divided by the number of questions answered. Subjects must answer at least 6 of 11 sub-items to be evaluable.

^[3] Baseline is defined as the last available measurement taken prior to the first dose of study drug.

Path\filename.sas ddmmmyyyy hh:mm

Programming note: Continue for Baseline^[3], Days 8, 15, 22, 29, 36, 41, 42, 43, 57

Listing 16.2.6.2
Gravimetric Sweat Production Measurements

Subject ID	Treatment Group	Visit	Gravimetric Assessment Performed?	Assessment Date (Study Day ^[1])	Right Axilla			Left Axilla			Total Sweat Weight ^[2]		
					Pre-test Weight	Start Time	End Time	Post-test Weight	Pre-test Weight	Start Time		End Time	Post-test Weight
xxx-xxxx	Vehicle / BBI-4000 5% / BBI-4000 10% / BBI-4000 15%	Visit 1 (Screening)	Yes / No		xx.x	hh:mm	hh:mm	xx.x	xx.x	hh:mm	hh:mm	xx.x	xx.x
		Visit 2 (GSP1)	...										
xxx-xxxx													

Abbreviation: GSP, gravimetrically measured sweat production

^[1] Time (days) relative to date of first dose of study drug

^[2] Total sweat weight is the sum of the post-test weights from the right axilla and left axilla.

^[3] Baseline is defined as the last available measurement taken prior to the first dose of study drug.

Path\filename.sas ddmmmyyyy hh:mm

Programming note: Continue for Visits 3 and 4, Baseline^[3], and Days 8, 15, 22, 29, 36, 41, 42, 43, 57

Listing 16.2.6.3
Hyperhidrosis Disease Severity Scale

Subject ID	Treatment Group	Visit	Date of Assessment (Study Day ^[1])	How would you rate the severity of your axillary hyperhidrosis?
xxx-xxxx	Vehicle / BBI-4000 5% / BBI-4000 10% / BBI-4000 15%	Visit 1 (Screening)	ddMMMyyyy (xx)	(1) My sweating is never noticeable and never interferes with my daily activities / (2) My sweating is tolerable but sometimes interferes with my daily activities / (3) My sweating is barely tolerable and frequently interferes with my daily activities / (4) My sweating is intolerable and always interferes with my daily activities
		Visit 4 (Rescreening)		
		...		
xxx-xxxx	...			

[1] Time (days) relative to date of first dose of study drug

[2] Baseline is defined as the last available measurement taken prior to the first dose of study drug.

Path\filename.sas ddmmmyyyy hh:mm

Programming note: Continue for Visits 3 and 4, Baseline^[2], and Days 8, 15, 22, 29, 36, 41, 42, 43, 57

Listing 16.2.6.4
Dermatology Life Quality Index- Axilla
Part 1 of 2

Question Number	Question Text	Responses
1	Over the last week, how itchy, sore, painful or stinging has your underarm skin been?	Very much A lot Almost none Not at all
2	Over the last week, how embarrassed or self-conscious have you been because of your underarm sweating?	Very much A lot Almost none Not at all
3	Over the last week, how much has your underarm sweating interfered with you going shopping or looking after your home or garden?	Very much A lot Almost none Not at all
4	Over the last week, how much has your underarm sweating influenced the clothes you wear?	Very much A lot Almost none Not at all Not relevant

Path\filename.sas ddmmmyyyy hh:mm

Programming note: Listing continues on next page.

Listing 16.2.6.4
Dermatology Life Quality Index- Axilla
Part 1 of 2

Question Number	Question Text	Responses
5	Over the last affected any social or leisure week, how much has your underarm sweating activities?	Very much A lot Almost none Not at all Not relevant
6	Over the last week, how much has your underarm sweating made it difficult for you to do any sport?	Very much A lot Almost none Not at all Not relevant
7	Over the last week, has your underarm sweating prevented you from working or studying?	Very much A lot Almost none Not at all Not relevant
	If "No", over the last week how much has your underarm sweating been a problem at work or studying?	A lot Almost none Not at all
8	Over the last week, how much has your underarm sweating created problems with your partner or any of your close friends or relatives?	Very much A lot Almost none Not at all Not relevant

Path\filename.sas ddmmmyyyy hh:mm

Programming note: Listing continues on next page.

Listing 16.2.6.4
Dermatology Life Quality Index- Axilla
Part 1 of 2

Question Number	Question Text	Responses
9	Over the last week, how much has your underarm sweating caused any sexual difficulties?	Very much A lot Almost none Not at all Not relevant
10	Over the last week, how much of a problem has the treatment for your underarm sweating been, for example by making your home messy, or by taking up time?	Very much A lot Almost none Not at all Not relevant

Path\filename.sas ddmmmyyyy hh:mm

Brickell Biotech, Inc.
BBI-4000-CL-203

Database Date/Analysis: DDMMYYYY/Draft
Page x of y

Listing 16.2.6.4
Dermatology Life Quality Index
Part 2 of 2

Subject ID	Treatment Group	Visit	DLQI Completed?	Assessment Date (Study Day ^[1])	Question Number										Total Score
					1	2	3	4	5	6	7	8	9	10	
xxx-xxxx	Vehicle / BBI-4000 5% / BBI-4000 10% / BBI-4000 15%	Visit 4 (Rescreening) Day 43 ...	Yes / No	ddMMMyyyy (xx)	0-3	0-3	0-3	0-3	0-3	0-3	0-3	0-3	0-3	0-3	0-30
xxx-xxxx															

Abbreviation: DLQI, Dermatology Life Quality Index-Axilla

Note: DLQI Total Score is calculated by summing the replies to Questions 1 through 10.

^[1] Time (days) relative to date of first dose of study drug

Path\filename.sas ddmmmyyyy hh:mm

**Listing 16.2.7.1
Adverse Events**

